Starting from the above considerations, and from the hypothesis that about 20 predictors will be evaluated for development of a risk score able to predict the severe coronavirus pneumonia outcome, the population size of the fitting population is set to N = 104+20=124 patients. In the procedure of splitting the data set into a fitting population and a validation population, the 50% of the entire sample will be used for the fitting step and the remaining 50% will be used as a validation population. A sample size of 248 patients will be therefore necessary.

Statistical Analysis

Primary Analysis

The data set will be split into a fitting population and a validation population by using the internal/validation/data-splitting method. The internal/validation/data-splitting method is chosen to limit the possible increase in bias that can occur with other techniques for internal validation such as

Bootstrapping technique if the original study population contains biases. The portion of the population used as fitting population for model development will be chosen randomly. The model will be then tested, in terms of its performance on the remaining validation population. Computation of the C statistic will be used to indicate the discrimination performance of the model. The C statistic represents a measure of the model's performance in terms of the model discrimination ability to separate subjects with different outcomes, and for the logistic model, it is equivalent to the area under the curve of the receiver operating characteristic (ROC) curve associated to the model (12) Values of C between 0.8 and 0.9 will be considered to give an excellent discrimination.

Computation of the probabilities: For each subject, both from the fitting population and the validation population, the probability of the studied outcome will be computed on the basis of the patient's covariate values. Each subject will be therefore characterized by the values of the covariate set, the outcome (coronavirus-severity, 0/1) and by the estimated probability of the outcome.

Computation of the C statistics: For both the fitting and the validation populations, the C statistics will be computed. The accuracy (percentage of true positive and negative on the total subjects) of the prediction model will be also computed.

Procedure repetition: The entire procedure (data splitting, model fitting, probability computation) will be repeated 200 times.

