Model fitting onto the whole population: The model will then be fitted using all the original data.

Results analysis: At the end of the procedure, the distribution of different indicators will be computed: for each variable, frequency histograms of the estimated coefficients along with their associated standard errors and levels of significance will be plotted. The importance index of each variable computed from each data splitting and model fitting will be also plotted.

The estimated coefficients from the whole population will be compared with the respective distributions (they should be centred around the estimates obtained on the whole sample); the distribution of the variability of the model coefficients indicates to which extent the results are dependent from the subpopulation used; comparison between the distribution of the C statistic computed on the fitting and the validation sample, along with the distribution of their Delta provide indication of the discrimination power of the model. It is expected that the C statistic is larger for the fitting sample than for the validation sample. A model with a high discrimination power presents small drops in the values of the C statistic when computed on the validation sample with respect to

values computed on the fitting sample for which the values are expected to be larger (C Delta distribution centred around the zero).

On the basis of the obtained results on the full model, the entire procedure is repeated on the subset of the most important variables to test and validate the final reduced model including the most meaningful predictors. Once the model validation is assessed the fitted coefficients used to compute the probability of the outcome on a generic patient will be those obtained from the "reduced model" fitting on the whole population sample.

Secondary analyses

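### The reduced model's validation C is biased upward because the validation patients help choose its variables, and the plan reads Delta, a measure of optimism, as a sign of discrimination

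*Combined protocol and SAP*

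**What the plan says.** All references are to the combined protocol and SAP, Statistical Analysis, Primary Analysis.

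- **Testing.** The sample is split in half at random. "The model will be then tested, in terms of its performance on the remaining validation population". Under Computation of the C statistics, "For both the fitting and the validation populations, the C statistics will be computed".
- **Band.** "Values of C between 0.8 and 0.9 will be considered to give an excellent discrimination". The sentence names neither the sample (fitting or validation) nor the model (full or reduced).
- **Loop.** Under Procedure repetition, "The entire procedure (data splitting, model fitting, probability computation) will be repeated 200 times". Variable selection is not in that list.
- **Delta.** Under Results analysis, the fitting and validation C distributions, "along with the distribution of their Delta provide indication of the discrimination power of the model". High discrimination is then associated with small drops: "A model with a high discrimination power presents small drops in the values of the C statistic when computed on the validation sample", glossed as "C Delta distribution centred around the zero". The same paragraph expects C to be larger in the fitting sample.
- **Reduced model.** "On the basis of the obtained results on the full model, the entire procedure is repeated on the subset of the most important variables", in order to test and validate the final model. Its coefficients, refitted on the whole sample, become the score.

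The plan does not define the importance index and does not say how many variables will be kept or by what cut-off.

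**The concern.** There are two linked problems.

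First, the subset of variables is fixed before the second round of splits, using results to which every patient contributed. Each validation half in that round therefore consists of patients whose outcomes helped choose the variables now being tested on them. The resulting C is not an independent check of the score.

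Second, the text invites the reader to take a small Delta as reassurance about discrimination. The reduced model will tend to show a small Delta for two reasons that have nothing to do with discriminating well: it has fewer coefficients, and selection on the validation patients raises its validation C.

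The primary end-point is a score to classify high-risk inpatients, and the reduced model's C will be the evidence offered for it. No external sample is planned. A careful reader of validation C would discount an inflated fitting C, but could not see the selection effect.

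**Working it through.** **The plan's own figure.** Sample size calculation: 104 + 20 = 124 for the fitting half; 124 × 2 = 248. Reproduced.

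**Step 1: whose data drive selection.** Each patient has probability 1/2 of being in a given fitting half. The probability of being in none of 200 fitting halves is 0.5^200, effectively zero. Importance results taken over the splits therefore use all 248 patients, and so would results from the whole-sample fit.

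**Step 2: Delta against discrimination.** Delta = fitting C − validation C. If C is 0.55 in both halves, Delta = 0. If C falls from 0.90 to 0.82, Delta = 0.08. Simulated studies (248 patients, 200 random 124/124 splits, 200 studies per event rate) show the same:

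| Assumed event rate | 10.1% | 22.7% | 40% |
|---|---|---|---|
| Weak model (1 predictor, log-odds 0.25 per SD): validation C | 0.55 | 0.56 | 0.56 |
| Weak model: Delta | 0.047 | 0.024 | 0.014 |
| Strong model (5 predictors, linear-predictor SD 1.5): validation C | 0.80 | 0.80 | 0.80 |
| Strong model: Delta | 0.061 | 0.036 | 0.029 |

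C differs by 0.24 to 0.25. Delta differs by only 0.012 to 0.015, and the weak model has the smaller Delta.

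**Step 3: size of the selection effect.** Inputs from the plan: 248 patients, 124/124 splits, 200 repetitions, a logistic model and the 19 predictors listed under Primary end-point. Assumptions:

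- Event rates: 49/487 = 10.1% and 15/66 = 22.7% come from the cohort cited in the Introduction; 40% is added.
- Predictors: independent standard normal, 6 with equal effect. The linear-predictor SD is 1.2 (moderate signal) or 0 (no signal).
- Selection: top 5 by mean |z| over the full-model fits, standing in for the undefined importance index.
- New-patient C: the reduced model fitted on all 248 and tested on 20,000 new patients per study.
- Nested: the top 5 chosen and refitted within each fitting half, then tested on the other half.
- 300 studies per rate.

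| Assumed event rate | 10.1% | 22.7% | 40% |
|---|---|---|---|
| Moderate: full-model Delta | 0.26 | 0.17 | 0.14 |
| Moderate: reduced-model Delta | 0.073 | 0.045 | 0.035 |
| Moderate: planned validation C | 0.764 | 0.753 | 0.752 |
| Moderate: new-patient C | 0.704 | 0.729 | 0.735 |
| Moderate: optimism (planned − new) | +0.060 | +0.024 | +0.017 |
| Moderate: nested validation C | 0.66 | 0.69 | 0.70 |
| No signal: planned validation C (new-patient C 0.50) | 0.62 | 0.59 | 0.58 |
| No signal: optimism | +0.12 | +0.09 | +0.08 |
| No signal: nested validation C | 0.50 | 0.50 | 0.50 |

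**Step 4: a separate simulation under other assumptions.** This used 20 predictors, 4 or 6 kept, event rates of 10, 20 and 30%, 100 datasets with 20 splits each (10 for nested), and 10,000 new patients. Weak signal means log-odds of 0.4 for three predictors and 0.15 for five, so the linear-predictor SD is √(3×0.16 + 5×0.0225) = 0.77. Strong means 0.9 for three and 0.3 for four, so the SD is √(3×0.81 + 4×0.09) = 1.67.

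| Signal | Planned validation C | New-patient C | Optimism | Nested validation C |
|---|---|---|---|---|
| None | 0.58-0.62 | 0.50 | +0.08 to +0.12 | 0.50-0.51 |
| Weak | 0.68-0.69 | 0.60-0.64 | +0.04 to +0.09 | 0.58-0.61 |
| Strong | 0.82-0.83 | 0.80-0.81 | +0.01 to +0.03 | 0.73-0.79 |

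In all 18 settings the mean planned validation C exceeded new-patient C, and reduced-model Delta was 18 to 40% of full-model Delta. With no signal, 10% events and 4 variables kept, fitting C was 0.727, planned validation C 0.621 and new-patient C 0.500. Delta shows a drop of 0.727 − 0.621 = 0.106 when the real drop is 0.727 − 0.500 = 0.227.

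**The case against.** **Much of this is wording.** The band sentence comes shortly after the statement that the model is tested on the validation half, so validation C is the natural reading. Both C values are reported and no planned decision hangs on the band. The quoted sentence says that good models show small drops, not that small drops prove a good model. This largely stands for the band. It does not rescue Delta, which the preceding sentence offers as an indicator of discrimination, and it does not touch the selection effect.

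**Nested selection can be further from the truth than the planned figure.** This stands. At linear-predictor SD 1.2 and event rates of 10.1 / 22.7 / 40%, a repeat simulation put nested C below new-patient C by 0.048 / 0.041 / 0.027, against planned optimism of 0.056 / 0.024 / 0.020. The nested root-mean-square error was the larger at 22.7% and 40%. At SD 1.8 nested C was low by 0.086 / 0.034 (10.1 / 22.7%). A reader might infer that nested C should replace the planned C; these results do not support that.

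**A reader might infer that a mediocre score would commonly be called excellent.** At SD 1.2 with 5 variables kept, fitting C was at least 0.8 with validation C below 0.8 in 62 / 36 / 28% of simulated studies. That signal lies just under the cut-off. Keeping 3 variables gives 23 / 3 / 0% and keeping 8 gives 72 / 73 / 60%. With 5 kept, SD 0.8 gives 36 / 5 / 1% and SD 2.5 gives 10 / 1 / 1%. The documents fix none of these inputs, so no such percentage can be attributed to this trial.

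**A reader might also infer that a poor full model would pass unnoticed.** It would not: its Delta of 0.14 to 0.26 in the moderate setting would expose it.

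**Conclusion.** The point holds for the reduced model. Its variables are selected with the patients who later validate it, so its validation C is biased upward on average. Its Delta is small relative to the full model's and understates the true loss. The association of a Delta near zero with high discrimination is wrong as written.

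The direction follows from the text and was consistent across the simulated settings. The size is an assumption. With 5 of 19 variables kept and event rates of about 10 to 40%, mean optimism is about +0.08 to +0.12 with no signal, +0.04 to +0.07 with weak signal, +0.02 to +0.06 with moderate signal and +0.01 to +0.03 with strong signal. Keeping 4 of 20 at 10% events raised the weak-signal figure to +0.09. Independent predictors and |z| as the importance index are further assumptions.

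If the predictors are strong, the effect is minor. If they are weak or events are few, it is large enough to change how the score is described. The band's missing sample is a clarification, not an error that would by itself mislead.

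**What to change.** 1. In Results analysis, delete the statement that a Delta centred around zero marks high discrimination and describe Delta as the estimate of optimism. State that the 0.8-0.9 band applies to the validation-sample C of the reduced model, not to fitting C.
2. Fix the selection rule in advance: which importance index, and how many variables or what threshold.
3. Add a run of the 200 splits in which that rule is repeated inside each fitting half. Report this nested validation C beside the planned one. Label the planned value optimistic, because selection used the validation patients. Label the nested value conservative, because each model is built on 124 patients and not 248. Call discrimination excellent without qualification only if both values fall in the band.

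The final score is still selected and fitted on all 248 patients.

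**Cost.** A few sentences in the SAP and somewhat more computation; no new data and no change in sample size. The reported C may look less favourable. With moderate to strong signal the nested value can understate the final score's C by about 0.03 to 0.09, so a good score could miss the unqualified label; the report should say so.

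### The reduced score is validated in the same patients who chose its variables, with selection not repeated, so its validation C tends to be too high unless a few strong predictors dominate

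*Combined protocol and SAP*

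**What the plan says.** The steps are all in the combined protocol and SAP, Statistical Analysis, Primary Analysis.

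- **Split.** Under Sample size calculation, "the 50% of the entire sample will be used for the fitting step"; the rest is the validation half.
- **Repetition.** Under Procedure repetition, "The entire procedure (data splitting, model fitting, probability computation) will be repeated 200 times". The bracket lists what is repeated, and variable selection is not in it.
- **Whole-sample fit.** Before any reduction, "The model will then be fitted using all the original data".
- **Summaries.** Results analysis collects coefficients, standard errors and significance levels over the splits. It adds: "The importance index of each variable computed from each data splitting and model fitting will be also plotted".
- **Reduction.** "On the basis of the obtained results on the full model, the entire procedure is repeated on the subset of the most important variables". The stated aim is "to test and validate the final reduced model including the most meaningful predictors".
- **Delivery.** "the fitted coefficients used to compute the probability of the outcome on a generic patient will be those obtained" from the reduced model fitted to the whole sample.

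The benchmark is: "Values of C between 0.8 and 0.9 will be considered to give an excellent discrimination". The text does not say which full-model result decides which variables stay, or how many. It describes no untouched hold-out set, external cohort or optimism correction.

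**The concern.** Held-out patients give an honest C only if they played no part in building the model being tested. Here the subset is fixed first, from results in all the patients, and the same patients are then split again. A variable that looks important partly by chance in these 248 patients will also look useful in any half of them, because that half contributed to the chance finding. Refitting the coefficients in each fitting half does not undo this.

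What is at stake is the main product. The primary end-point is a simple severity score, and the reduced model is that score. Its validation C is likely to be read as the score's discrimination. The planned comparison of C between fitting and validation halves cannot reveal the problem, because both halves use the same pre-selected variables. The 0.8 to 0.9 band is a descriptive label and not a success rule, so the harm is an overstated performance figure rather than a wrong go/no-go decision.

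**Working it through.** **1. The plan's own figure.** Fitting population: 104 + 20 = 124. Total: 124 / 0.5 = 248. Both reproduce.

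**2. Whose outcomes drive selection.** With 50/50 splits, the chance that a given patient is in no fitting half over 200 splits is 0.5^200, about 6 × 10^-61. The whole-sample fit uses everyone anyway. Whichever listed result drives the choice, essentially every patient's outcome has been used.

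**3. Size of the effect, by simulation.**

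- From the documents: n = 248, about 20 predictors, 50/50 splits, logistic model.
- Assumed: 5 variables kept, ranked by mean |z| over the full-model fits; independent predictors; event rates of 10/20/30% (about 25/50/74 events); a ridge penalty of 0.1 so that separated fits converge. For orientation only, the background cohort in the Introduction had 10.1% severe at admission and 15/66 = 22.7% progressing. Neither is a planning value.
- True C: the delivered model (selected variables, refitted to all 248) applied to 20,000 new patients.
- Excess = mean validation C under the plan minus true C. 300 datasets × 30 splits; standard error 0.002 to 0.004.

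| Assumed signal (log odds ratio per SD) | 10% events | 20% | 30% |
|---|---|---|---|
| none (boundary case) | 0.12 | 0.10 | 0.08 |
| twenty at 0.2 | 0.10 | 0.08 | 0.07 |
| five at 0.35 | 0.09 | 0.05 | 0.04 |
| five at 0.5 | 0.06 | 0.02 | 0.02 |
| three at 0.9 | 0.02 | 0.01 | 0.01 |
| five at 0.8 | 0.03 | 0.00 | 0.00 |

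For five at 0.35 the levels are 0.70/0.68/0.68 reported against 0.61/0.64/0.65 true. For five at 0.5 they are 0.75/0.75/0.74 against 0.69/0.72/0.73. Excesses were computed before rounding.

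**4. Is patient reuse the cause?** When the same rule picked the variables in an independent 248 patients, and 50/50 validation was then done in the study patients, the error was -0.025 to +0.003 over the same 18 settings. The positive excess therefore comes from reusing the patients. Splitting alone is slightly pessimistic, because each model is fitted on half the sample.

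**5. Sensitivity.**

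- Ranking by the whole-sample fit changes the table by at most 0.011.
- With 19 predictors typed as in the Primary end-point list (7 binary, 12 continuous), 3 or 8 kept, correlation 0.3, or a lighter ridge, the excess was 0.07 to 0.12 with no signal, 0.02 to 0.08 at 0.35, 0.01 to 0.07 at 0.5 and -0.005 to 0.04 at 0.8.
- With the plan's full 200 splits (150 datasets, 8 settings) it was 0.096 with no signal and 0.050 for five at 0.35 (both at 20% events), 0.06/0.03/0.02 at 0.5 and 0.02/0.00/0.00 at 0.8.
- Over all 18 + 60 + 8 = 86 settings the mean error ran from -0.005 to +0.123. It was above zero in 82; the other four were -0.001 to -0.005, all with five at 0.8 and 20 to 30% events.
- A separate simulation (correlation 0.2, 4 or 8 kept, event rates 20% and 35%, 60 datasets × 30 splits) found the planned C above the true C on average in all 20 scenarios: +0.060 to +0.077 with noise, +0.016 to +0.055 with weak to graded effects, +0.004 to +0.013 with four strong predictors.

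**6. Selection repeated inside each fitting part.** Nested 80/20 had mean error -0.024 to +0.011 over the 86 settings. Nested 50/50 was too low when there was signal: -0.05/-0.05/-0.04 for five at 0.5 and -0.06/-0.05/-0.04 for five at 0.8.

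**The case against.** **The bias is small where the label matters.** In the equal-effect settings with five real predictors, a C of 0.8 is reached only near a log odds ratio of 0.8, where the excess is 0.03/0.00/0.00. The large figures belong to weak or absent signal, and the Introduction reports earlier associations for several candidates. This stands, and it limits the severity. It is not general: with graded effects (1.2, 0.7, 0.5, 0.4, 0.3 and five at 0.1) and 20% events, the plan gave 0.818 against a true 0.797. Nor can the investigators know beforehand that they are in the strong-signal case.

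**Nesting trades bias for variance.** This also stands. Root mean squared error, nested 80/20 against the plan, at 10/20/30% events, is 0.074/0.050/0.049 against 0.080/0.053/0.042 for five at 0.5, and 0.068/0.040/0.034 against 0.053/0.035/0.029 for five at 0.8. In the latter case, nesting more often reports below 0.80 when the true C is at least 0.80 (30/20/16% against 11/10/13%). The gain is at weak signal (20% events): 0.054 against 0.103 with none, 0.052 against 0.063 for five at 0.35. The case for nesting is removal of bias, not uniformly better accuracy.

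**A selection-free figure is already planned.** The full model's validation C is not inflated. It describes a model with about 20 predictors, however, and not the delivered score: for five at 0.5 it is 0.65/0.68/0.69, against 0.69/0.72/0.73 for the delivered model.

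**Other readings of the text.** One could read selection into the repeated procedure, but the bracket that defines it and its application to an already chosen subset speak against that. Clinical judgement could soften outcome-driven selection, but the plan bases the choice on full-model results. The Secondary analyses are exploratory and concern other classifiers or univariate associations, so they do not repair this.

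**Conclusion.** The concern holds. As written, the reduced model's validation C leaves out selection optimism, and on average it is too high unless a few strong predictors are all retained; then the excess is small, nil or very slightly negative.

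Confidence is high for the structure and direction, not for the size. Under the assumptions above, the excess runs from about zero to 0.12, and is mostly 0.02 to 0.09 for five predictors of weak to moderate strength. These figures depend on the assumed event rate, number kept, ranking by |z| and signal pattern, none of which the documents give. The full model's C and the sample size of 248 are unaffected. The point should be corrected before analysis, as a matter of how performance is estimated and reported.

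**What to change.** In Results analysis, change the reduction step as follows.

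1. Fix one ranking measure and one retention rule in advance, so that selection can be repeated by program.
2. For the reduced model, run ranking, selection and fitting inside the fitting part of each of the 200 repetitions, and compute C in the held-out part.
3. Use a larger fitting fraction for this step, for example 80/20: 0.8 × 248 = 198 fitting patients, above the plan's 124. If nested 50/50 is also shown, call it a conservative lower figure and not the performance estimate.
4. Report the nested C as the internal-validation performance, beside the full model's validation C and the frequency with which each variable was selected. State that the nested figure is corrected for selection but noisier.
5. Keep the final whole-sample fit of the reduced model as planned.

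**Cost.** SAP wording and a few lines of code, with no extra patients or data. It departs from the 50/50 split for this one step. Each 80/20 split holds out about 50 patients (about 5/10/15 events at 10/20/30%), so single splits are noisy; averaging over 200 repetitions mitigates this. The reported C will usually be lower, and with strong predictors it may be slightly less accurate than the planned figure.

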Nasopharyngeal swab samples will be taken for quantitative real-time polymerase chain reaction to make diagnosis of Covid19 (2 repeated tests).

Data collected include time of type of symptoms (cough, fever, dyspnea, conjunctivitis, diarrhea, asthenia, arthralgia) and duration, comorbidities (presence of diabetes, hypertension, cardiovascular disease), PaO2/FiO2 ratio, age, sex, height, weight, triglycerides, complete blood count, D-dimer, lactic acid dehydrogenase (LDH), high-sensitivity C-reactive protein (hs-CRP), albumin, and ferritin. The duration of the follow-up will be 28 days from the patient's hospitalization or until his/her discharge or death.

Primary end-point

The primary end-point is to identify the best predictors of critical coronavirus pneumonia and to realize a simple severity score able to early classify high-risk individuals admitted to Internal Medicine Department for COVID-19 disease, needing an intensive approach.

The evaluated predictors for the score assessment are the following: symptoms duration, type of symptoms (cough, fever and dyspnea), comorbidities (presence of diabetes, hypertension, ischemic heart disease), PaO2/FiO2 ratio, age, sex, body mass index (BMI), triglycerides, white cell count, lymphocyte count, D-dimer, lactic acid dehydrogenase (LDH), high-sensitivity C-reactive protein (hs-CRP), albumin, and ferritin. These parameters were collected at admission.

Sample size calculation

The sample size determination is based on the following considerations:

1) the objective of the study is that of finding the best predictors of severe coronavirus pneumonia outcome;

 the study sample will be constituted by inpatients cases of COVID-19 admitted to Internal Medicine Department of Fondazione Policlinico A. Gemelli IRCCS;

3) in order to test the predictive ability of the developed score the study sample will be split into a fitting population and a validation population by using the internal/validation/data-splitting method 4) the following rule-of-thumb will be considered: the power for a test of a medium-sized partial correlation between y and a predictor, holding all other predictors constant, is approximately .80 if N = 104 + m, where m is the number of predictors (11).

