Secondary analyses include the use of other classification procedures to compare results from the primary analysis. One of the classification procedures that will be used to classify patients with severe and non-severe coronavirus pneumonia outcome, on the basis of the collected variables, will be the Partial Least-Squares Discriminant *Analysis (PLS-DA)*. A cross validation approach will be followed and the optimal model with the optimal number of PLS components will be derived. The Q2 value, the ROC AUC and the derived misclassification error, by the classification Youden criterium, will be used to quantify the classification goodness. A permutation approach, including 1000 random permutations, will be used in order to associate a P level to the obtained Q2 value. Random forest classification procedure, which is based on learning algorithms, will be also tested following the same procedure of splitting the entire sample into a training set and a test set. Univariate analyses studying the association between severity and predictors will be conducting using Chi-Squared tests or Fisher exact tests when appropriate or univariate logistic regression models for quantitative variables. Secondary analyses will have only an explorative purpose.

REFERENCES

5) Dong L et al. Discovering drugs to treat Coronavirs Disease 2019 (COVID-19). Drug Discov Ther 2020

7)Womg CK, et al. Plasma inflammatory cytokines and chemokines in severe acute respiraoty syndrome. Clin Exp Immunol 2004;

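### The final equation gives individual probabilities after variable selection and refitting on the same patients, and no planned measure checks their calibration

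*Combined protocol and SAP*

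**What the plan says.** The primary end-point is to find the best predictors and build "a simple severity score able to early classify high-risk individuals". The Primary Analysis splits the 248 patients at random into halves of 124, fits the model in one half and tests it in the other, 200 times. The steps listed for repetition are splitting, fitting and computing probabilities; choosing variables is not among them.

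After the full model has been run, "the entire procedure is repeated on the subset of the most important variables to test and validate the final reduced model". The final equation is then fixed: "the fitted coefficients used to compute the probability of the outcome on a generic patient will be those obtained from the" reduced model, fitted on everyone.

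Two performance measures are named for this model. One is discrimination: "Computation of the C statistic will be used to indicate the discrimination performance of the model", with the difference between fitting and validation halves (Delta C). The other is classification: "The accuracy (percentage of true positive and negative on the total subjects) of the prediction model will be also computed". Histograms of coefficients, standard errors, significance levels and importance indices are added. The Q2 statistic, ROC AUC and misclassification error appear only under Secondary analyses, which are exploratory.

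The raw material for a calibration check is already planned: "For each subject, both from the fitting population and the validation population, the probability of the studied outcome will be computed".

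**The concern.** Variables kept because their estimated effects looked large, and then refitted on the same patients, have coefficients that are too large on average. The linear predictor is over-spread: high risks are overstated and low risks understated in new patients. The plan commits to a probability for an individual patient, so this is an error in a stated output.

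The named measures do not capture it. C and Delta C depend only on ranking. Accuracy needs a cut-off, which is not stated. The secondary classifiers' measures belong to other models. At stake are the probabilities themselves, and any threshold later fixed as an absolute probability (the plan sets none).

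**Working it through.** **Plan's own figure.** Fitting half: 104 + 20 = 124. Total: 124 / 0.5 = 248, as stated. (The list under the primary end-point counts to 19 single terms, giving 2 × (104 + 19) = 246.) The rule concerns power for a partial correlation. At N = 124 with 20 predictors and two-sided 0.05 (assumed), power is 0.81 for a partial correlation of 0.25, consistent with the rule. It says nothing about calibration.

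**Measure.** In new patients, logit(risk) = a + b × (linear predictor of the fitted equation). b is the calibration slope: 1 is ideal, below 1 means too extreme.

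**Inputs not in the plan.** Event rate, number of variables kept and definition of importance are not given, and the logistic form is only implied. Assumed event rates are 10.1% (49/487) and 22.7% (15/66), both from the cohort cited in the Introduction and neither being this study's outcome, plus 30% and 40%. Events in 248:
- 248 × 0.101 ≈ 25
- 248 × 15/66 ≈ 56
- 248 × 0.30 ≈ 74
- 248 × 0.40 ≈ 99

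**First simulation.** 400 studies of 248 per cell; 19 candidates (7 binary, 12 continuous, latent correlation 0.2); underlying C 0.82. The variables with the largest absolute Wald z in the full model are kept and refitted on the same data. The slope is measured in 8,000 new patients. Median slopes:

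| True effects, number kept | 10.1% | 22.7% | 30% | 40% |
|---|---|---|---|---|
| All 19, decaying; 5 kept | 0.56 | 0.71 | 0.73 | 0.75 |
| 5 equal; 5 kept | 0.60 | 0.78 | 0.80 | 0.84 |
| 3 strong; 5 kept | 0.64 | 0.81 | 0.81 | 0.82 |
| 3 strong; 3 kept (mild case) | 0.73 | 0.92 | 0.92 | 0.94 |

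Keeping 8 gives 0.52 to 0.77. The slope is below 1 in 88–100% of studies with 5 kept and in 69–92% in the mild case.

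**Second simulation, different design.** 20 predictors, 10 with an effect, true C 0.75 or 0.85, 300 studies per scenario, rates 10% to 40%. Median slopes are 0.49 to 0.83 with 5 kept and 0.43 to 0.77 with 8 kept. With the five strongest predictors fixed in advance they are 0.78 to 0.95, so most of the shortfall comes from selection.

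**On the risk scale.** Mean predicted against true risk in the top predicted tenth (first simulation):
- 5 kept: 47–48% against 31–34% at the 10.1% rate; 89–90% against 82–86% at the 40% rate.
- Mild case: 43% against 34% at 10.1%; 70% against 68% at 22.7%; 80% against 78% at 30%; 89% against 87% at 40%.

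**What the planned outputs would show.**
- Full-model Delta C: about 0.11 to 0.25 across runs, largest where events are fewest.
- Reduced-model Delta C: only about 0.02 to 0.06, with left-out C of 0.80–0.82, inside the plan's 0.8 to 0.9 band for excellent discrimination. The left-out patients have already helped choose the variables. In the second simulation, left-out C under this scheme was 0.74–0.83, against 0.69–0.82 in independent patients.
- Accuracy at an illustrative cut-off of 0.5: differs by at most 0.6 percentage points between the unshrunk and a shrunk equation.
- Coefficient histograms: full-model half-sample coefficients of the top five variables were 1.13–1.21 times the whole-sample values at rates of 22.7–40%, and 1.5–1.6 times at 10.1%. This shows small-sample inflation but not selection bias.

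**The case against.** A reader might infer that nothing in the plan would warn the user. The documents do not support that. The whole procedure runs first on the full model, whose Delta C would be visibly large. The plan also gives a benchmark (a Delta distribution centred on zero), compares split coefficients with the whole-sample fit, and adopts the final coefficients only after validation has been assessed. These are real signals of overfitting. What remains is that they concern the full model, carry no numeric limit or correction, and do not measure error in the reduced equation's probabilities.

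A reader might also infer that the score would misorder or misclassify patients. Uniform over-spread changes neither ranking nor a cut-off read from the same model's ROC curve, and the primary end-point asks for a score that classifies. The harm is confined to the probabilities, but the plan does promise those.

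It is fair to object that the absence of shrinkage is read from silence: the plan says only that the coefficients are fitted. It is also fair that the size rests on assumptions, and that 10.1% is severity at admission, not a later outcome. Both objections limit how strongly the point can be put. Neither supplies a calibration measure.

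**Conclusion.** The point holds in direction and in what is missing. Selection and refitting on the same 248 patients, with no shrinkage mentioned, is expected to give probabilities that are too extreme, and no planned measure assesses calibration of the reduced equation. The size is not fixed by the documents. Median slopes of about 0.5 to 0.94 follow from assumed event rates of 10–40%, 3 to 8 variables kept, selection by Wald z and an underlying C of 0.82; the lowest value in the second design, 0.43, needs a true C of 0.75, 10% events and 8 kept. With few true predictors, few kept and 56 or more events, the effect is slight. Quoting one figure as the expected miscalibration, or treating shrinkage as indispensable, would go beyond the documents. The plan should be changed on this point, but its ranking results do not fall with it.

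**What to change.** **Requested.** State a fixed automatic selection rule and apply it afresh inside each fitting half of the 200 splits. On the left-out half, report calibration intercept, slope and plot beside C. State that these describe 124-patient fits, not the 248-patient equation. In simulation with 5 kept, the median left-out slope was 0.37–0.69 with selection repeated and 0.70–0.87 with variables fixed beforehand; neither equals the slope of the final equation, so neither should serve as its shrinkage factor. Cost: SAP wording, some computing and a less favourable reported performance. No new data are needed.

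**Optional.** Shrink the 248-patient equation by one pre-stated method, for example a uniform factor from repeated cross-validation with selection repeated each time and the intercept re-estimated. This respects the stated reservation about bootstrapping (splitting was "chosen to limit the possible increase in bias that can occur with other techniques for internal validation such as" bootstrapping), and cross-validation is already used for PLS-DA ("A cross validation approach will be followed"). State that the resampling only estimates the factor and does not replace the data-splitting validation. Cost: coefficients read less well as odds ratios, and the correction is imprecise if events are few. At about 25 events the corrected slope ran from 0.71 to 2.20 (10th to 90th percentile). In the mild case at rates of 22.7% or more the gain is small, with slight over-correction (median 1.02–1.06). If shrinkage is not adopted, present the equation's probabilities as not calibrated.
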